2.6 USE OF RESCUE MEDICATION

2.6.1 Available data

For each administration of rescue medication, the start and end date(time) and the number of puffs will be recorded.

2.6.2 Derivation rules

The following parameters will be derived:

- Mean use of rescue medication (puffs) = total number of puffs of rescue medication during the first 3h post-dose

2.6.3 Presentation of results

The number and percentage of subjects with use of rescue medication in the first 3h post-dose will be presented by treatment using frequency tabulations.

[figure not shown]
Mean use of rescue medication in the first 3h post-dose will be summarised by means of descriptive statistics by treatment.

	Statistical Analysis Plan	
CLI-05993AB6-07		Final 1.0 of 22DEC2022

All rescue medication data will be listed.

2.7 PHYSICAL EXAMINATIONS

Abnormal physical examination findings will be listed.

Statistical Analysis Plan

CLI-05993AB6-07

Final 1.0 of 22DEC2022

	Statistical Analysis Plan	
CLI-05993AB6-07		Final 1.0 of 22DEC2022

4. GENERAL CHARACTERISTICS ANALYSES

4.1 SUBJECT DISPOSITION

The following subject data will be tabulated by treatment sequence:

- The number of screen failures
- The number and percentage of subjects who completed or discontinued the study as documented on the study termination page and the number and percentage of subjects for each study discontinuation reason
- The number of subjects in each analysis set per period
- The number of subjects enrolled, randomised, completed, and discontinued by site
- The number and percentage of subjects who entered, completed, or discontinued each study period

All information collected in the CRF concerning allocation, code breaking, study discontinuation (discontinuations due to COVID-19 will be flagged) and information on phases and periods, dates of first signed informed consent, last visit and last contact (over the whole study) will be listed.

4.2 PROTOCOL DEVIATIONS AND ELIGIBILITY

The number and percentage of subjects with important protocol deviations, per category and type, will be tabulated, by treatment and overall.

All available information concerning protocol deviations (protocol deviations related to COVID-19 will be flagged), violations on eligibility criteria (only violated eligibility criteria having DV.DVCAT = 'INCLUSION/EXCLUSION CRITERIA') and restrictions will be listed.

4.3 DEMOGRAPHIC AND OTHER BASELINE CHARACTERISTICS

4.3.1 *Available data*

The following parameters will be available:

- Demographics: women of childbearing potential (yes / no / post-menopausal), age, sex, race, BMI, height and weight at screening, date of birth, and date of signing informed consent form (ICF), smoking status, duration and number of pack-years
- Screening tests: vital signs, local 12-lead ECG, lung function, reversibility test and ACQ-5
- Baseline disease characteristics: date of first diagnosis, asthma medication at study entry, exacerbation history (number of exacerbations in the 12 months before screening and date of the most recent exacerbation ended, treatment, hospitalisation, emergency room)

Statistical Analysis Plan

CLI-05993AB6-07

Final 1.0 of 22DEC2022

4.3.2 *Derivation rules*

The following parameters will be derived:

- Age categories:
 - ≥ 18 and < 65 years
 - ≥ 65 and < 85 years
- Time since first diagnosis (years): (date of ICF – date of first diagnosis)/365.25
 - Note: Partially missing dates will be imputed as specified in section 5.3.2
- Time since most recent exacerbation (months): (date of ICF – date of most recent exacerbation ended)/30.4375
 - Note: Partially missing dates will be imputed as specified in section 5.3.2
- Mean values of the duplicates (blood pressure parameters) will be calculated and rounded as detailed in section 5.3.4. Records belonging to the same duplicate will be identified using the visit and time point. In case of only one assessment available for the specific time point, its result will be considered.
- Mean values of the triplicates (ECG parameters) will be calculated and rounded as detailed in section 5.3.4. Records belonging to the same triplicate will be identified using the visit and time point. All records of the triplicate will be used to calculate the mean, even if less or more than the expected three.

4.3.3 *Presentation of results*

Demographics will be presented by treatment sequence and overall using descriptive statistics for age, height, weight, BMI, smoking duration and number of pack-years (current and ex-smokers only) and frequency tabulations for sex, race, age category and smoking status.

Baseline disease characteristics will be presented by treatment sequence and overall using descriptive statistics for time since first diagnosis, time since most recent exacerbation ended and number of exacerbations in the last 12 months and frequency tabulations for asthma medication category at study entry, number of exacerbations in the last 12 months, last exacerbation treatments, hospitalization and emergency room.

In addition, the following parameters will be presented by treatment sequence and overall using descriptive statistics:

- vital signs at screening and Period 1 Day 1 pre-dose;
- local 12-lead ECG at screening and Period 1 Day 1 pre-dose;
- lung function at screening and Period 1 Day 1 pre-dose;
- reversibility test at screening (FEV₁ Reversibility (mL) and FEV₁ Reversibility (%));
- ACQ-5 at screening and Period 1 Day 1 pre-dose.

	Statistical Analysis Plan	
CLI-05993AB6-07		Final 1.0 of 22DEC2022

All demographic data, baseline disease characteristics and screening tests (except when listed in the safety part, i.e. vital signs, local 12-lead ECG, lung function) will be listed.

4.4 MEDICAL HISTORY AND CONCOMITANT DISEASES

4.4.1 *Available data*

Medical history and concomitant diseases findings are coded using the medical dictionary for regulatory activities (MedDRA) into system organ classes and preferred terms. For each finding (MH.MHCAT is 'GENERAL MEDICAL HISTORY'), a start and stop date or ongoing flag is collected.

The following selection will be performed:

- Medical history finding: not ongoing at informed consent (MH.MHENRTPT is 'BEFORE')
- Concomitant disease finding: still ongoing at informed consent (MH.MHENRTPT is 'ONGOING' or missing)

4.4.2 *Presentation of results*

Medical history and concomitant diseases will be tabulated separately by treatment sequence and overall. Each table will show:

- The number and percentage of subjects with findings
- The number and percentage of subjects with findings by system organ class and preferred term

All medical history and concomitant diseases data will be listed separately.

4.5 PROCEDURES AND MEDICATIONS

4.5.1 *Available data*

All procedures are coded into system organ classes and preferred terms using the medical dictionary for regulatory activities (MedDRA). For each procedure, start and stop dates or ongoing flag are collected.

All medications are coded using WHO Drug. ATC coding up to level 5 is available in the clinical database. For each medication, a start date(time) and stop date(time) or ongoing flag are collected.

4.5.2 *Derivation rules*

Based on their start and stop date(time), procedures and medications will be allocated to each phase / period during which they were performed/administered. A procedure/medication can therefore be reported in more than one phase or period.

Phases and periods are defined in section 5.2.1. Procedures/medications with (partially) missing dates will be allocated to each phase / period unless the available parts of the procedure/medication start or stop date(time) provide evidence that the procedure/medication was not performed/taken during that phase / period.

	Statistical Analysis Plan	
CLI-05993AB6-07		Final 1.0 of 22DEC2022

Based on their start and stop date(time) procedures and medications will be allocated to one of the following categories:

- Prior: the procedure/medication stopped prior to first study drug administration
- Maintained: the procedure/medication started before first study drug administration and was ongoing at first study drug administration
- Concomitant: the procedure/medication started at or after first study drug administration

For procedures/medications with (partially) missing date(time)s not allowing allocation to any of the categories, a worst-case allocation will be done based on the available parts of the medication/procedure start or stop date(time). The medication/procedure will be allocated to the first category allowed by the available data, according to the following order:

- Concomitant
- Maintained
- Prior

Note: these procedures/medications will only be allocated to the phases / periods that match the worst-case allocated category.

4.5.3 Presentation of results

Procedures:

All procedures data will be listed.

Medications:

The number and percentage of subjects with medications and the number and percentage of subjects with medications by anatomical main group (level 1), therapeutic subgroup (level 2), chemical subgroup (level 4), and preferred name will be tabulated per category (prior, maintained, and concomitant); by treatment (sequence for prior medications) and overall. Blank ATC levels and preferred names, if any, will be shown as 'Not Available' in the tables.

Subjects having more than one medication allocated to the same category within the same treatment (sequence), anatomical main group, therapeutic subgroup, chemical subgroup, and preferred name will be counted only once.

All medications data will be listed.

4.6 EXPOSURE TO STUDY DRUG

4.6.1 Available data

For each study drug administration, the start date(time)s, the number of correct and incorrect inhalations and the reason for incorrect inhalations. In addition, data on training with inhalers is collected.

4.6.2 Presentation of results

All exposure and training with inhalers data will be listed.

	Statistical Analysis Plan	
CLI-05993AB6-07		Final 1.0 of 22DEC2022

5. GENERAL METHODOLOGY

5.1 ANALYSIS SETS

5.1.1 *Analysis sets*

The following analysis sets will be considered in the statistical analysis:

Enrolled Set (ENR): subjects who *signed an informed consent* to participate in this study

Randomised Set (RND): subjects who were *randomised* into this study

Safety Set (SAF): subjects who were randomised and *received at least one dose of study drug*

Per Protocol (PP) Analysis Set: subjects from the SAF, excluding the subjects having important protocol deviations impacting the analysis set

Notes:

- Having signed an informed consent is defined as having a complete informed consent signature date in the database.
- Randomised is defined as having a randomisation date in the database or any information to confirm randomisation.
- Having received at least one dose of study drug is defined as having an exposure date or any information confirming exposure.
- Exact definition of important protocol deviations concerning PP will be discussed by the clinical team and described in the DRR. The subjects to be excluded from PP analysis set will be defined in the DRR.

Unless stated otherwise, the SAF will be used for the general characteristics, safety [REDACTED] tables, listings and figures. The variables assessing the primary study objective will also be analysed considering the PP, for sensitivity purposes.

Since a cross-over design will be used, the inclusion in the analysis sets will be defined at subject level on a per-period basis and at subject level overall (in case all periods are affected). In case of important protocol deviations impacting specific time points, only the affected data at the specific time point will be excluded from the applicable analysis sets. These cases will be documented in the DRR.

5.1.2 *As planned versus as actual analysis*

For analyses done on the safety analysis set and on PP analysis set (excluding general characteristics analyses), the actual treatment of the subject will be considered. In addition, the actual treatment will be presented in all listings.

For all other analyses, the planned treatment (sequence) will be used.

	Statistical Analysis Plan	
CLI-05993AB6-07		Final 1.0 of 22DEC2022

5.2 PHASES, PERIODS AND TIME POINTS

5.2.1 *Phases and periods*

Adverse events, medications, and procedures will be allocated to phases and periods. All other analyses will not be allocated to phases and periods. Instead, the visit and time point labels indicated on the subject's case report form (CRF) will be used to allocate the assessments to the correct treatment. Early termination and follow-up visit assessment will be allocated to the last administered treatment.

Adverse events and medications:

Phase	Period	Start	End
Screening		Date of signing the informed consent form (ICF), with 00:00 added as time part	First administration date(time) in period 1 – 1 minute
Treatment	Period 1	First administration date(time) in period 1	First administration date(time) in period 2 – 1 minute
	Period 2	First administration date(time) in period 2	Date of last contact, with 23:59 added as time part

Per definition, and for each subject, the first phase starts on the date of the earliest available ICF signature, with 00:00 added as time part. The last available phase/period ends on the date of last contact, with 23:59 added as time part.

Procedures:

Phase	Period	Start	End
Screening		Date of signing the informed consent form (ICF)	First administration date in period 1 – 1 day
Treatment	Period 1	First administration date in period 1	First administration date in period 2 – 1 day
	Period 2	First administration date in period 2	Date of last contact

Per definition, and for each subject, the first phase starts on the date of the earliest available ICF signature. The last available phase/period ends on the date of last contact.

All tables and figures will present treatments/sequences rather than periods.

AEs, medications and procedures will be allocated to phases and periods as described in sections 2.1.2 and 4.5.2 respectively.

	Statistical Analysis Plan	
CLI-05993AB6-07		Final 1.0 of 22DEC2022

5.2.2 *Baseline and change from baseline*

The baseline value is a non-missing value before the first administration of any study drug.

The following table summarizes the baseline definition for each parameter:

Parameter	Baseline
Vital signs	Day 1 pre-dose (of each treatment period)
ECG parameters	Day 1 pre-dose (of each treatment period)
Lung function	Day 1 pre-dose (average of 45 min and 15 min pre-dose measurements of each treatment period)

Note: decisions on whether a different baseline should be used in the analysis will be fully documented in the DRR.

Change from baseline is defined as:

Change from baseline at time point t = value at time point t – baseline value.

Relative change from baseline at time point t is defined as follows:

- When baseline value is not zero: $100 * ((\text{value at time point t} - \text{baseline value}) / \text{baseline value})$
- When baseline value is zero: not calculated

5.2.3 *Relative day*

Relative days (DY) will be calculated according to the following rule:

- Concerned date < reference date: DY = concerned date – reference date
- Concerned date \geq reference date: DY = concerned date – reference date + 1

The reference date is the date of first administration of study drug (in the study and in each period).

5.2.4 *Analysis visits*

The analysis will use the visits and time points indicated on the subject's CRF, while for the timepoints related to the vital signs, ECG and spirometry assessments a windowing approach will be used (see time window definitions below).

The screening value is the last available and non-missing value before Period 1 Day 1. This value corresponds to the screening visit, except in case of retesting. Reason for this approach is the use of retest results for subject eligibility assessment.

Unscheduled assessments will not be used in the analysis unless it is selected as screening value, or per time window definitions below.

The unscheduled assessments will be checked during the DRM before database lock, and any different approach to the rule defined above will be documented in the DRR.

Baseline is defined in section 5.2.2.

All scheduled and unscheduled assessments will be listed. Early termination and follow-up visits will be listed only, unless otherwise specified.

Statistical Analysis Plan

CLI-05993AB6-07

Final 1.0 of 22DEC2022

Except when defined by time windows, the analysis visit labels will be assigned using the following rules:

- All planned screening, re-screening, eligibility re-check, etc. visits occurred during the screening phase will be presented as 'Screening'.
- All planned visits occurred during a scheduled day, will be presented as 'Day x' (x = study day, e.g. 'Day -1', 'Day 1', etc.)
- Early termination visits will be presented as 'Early Termination'
- Follow-up visits will be presented as 'Follow-up'
- Unscheduled visits will be presented as 'Unscheduled' unless the decision to reallocate the visit is fully documented in the DRR. In case of reallocation, the unscheduled visit will be presented with the same label as the replaced planned visit (see rules above)
- Other visits not covered by the rules above will be presented using similar labels to the ones used in SDTM (XX.VISIT)

The analysis time point labels for spirometry, vital signs and ECG parameters, will be assigned using the following time windowing rules.

Next to the screening value, all assessments, including unscheduled assessments, will be allocated to analysis windows. Tables will present the analysis windows as defined below and listings will present the analysis windows, as well as the CRF visits.

Allocation of assessments will be done according to the following tables:

Spirometry:

Analysis time point window	Target time from dose of study drug per period (minutes)	Time interval (minutes)
45min Pre-dose	<0	Day 1, before study drug
15min Pre-dose	<0	Day 1, before study drug
5min	5	[3 ; 10)
15min	15	[10 ; 23)
30min	30	[23 ; 45)
1h	60	[45 ; 75)
1.5h	90	[75 ; 135)
3h	180	[135 ; 240]

Notes:

- Target time and time interval will be calculated in each treatment period from the first inhalation for pre-dose assessments and from the last inhalation for post-dose assessments.
- The 45min pre-dose and 15min pre-dose assessments will first be allocated to analysis windows before calculation of the pre-dose mean value.

	Statistical Analysis Plan	
CLI-05993AB6-07		Final 1.0 of 22DEC2022

Vital signs and ECG:

Analysis time point window	Target time from dose of study drug per period (minutes)	Time interval (minutes)
Pre-dose	<0	Day 1, before study drug
45min	45	[15 ; 75)
1h 45min	105	[75 ; 135)
2h 45min	165	[135 ; 240]

Note: Target time and time interval will be calculated in each treatment period from the first inhalation for pre-dose assessments and from the last inhalation for post-dose assessments.

Per parameter and analysis window, the value closest to the target time will be used in analysis tables and figures, other values will only be listed. If more than one value is located at the same distance from the target, then the latest in time will be selected. The value latest in time will be identified using, in order of preference, the assessment time, the visit and time point label or the group identifier. Missing values are removed before the selection is made.

Partially missing assessment dates or times disabling allocation to analysis windows will not be imputed and thus these assessments will not be considered in the per-time point analysis, except for the derivation of the worst-case.

5.2.5 *Worst-case*

A worst-case analysis visit (presented in the analysis as 'At Any Time Point', or similar) will be created for parameters for which abnormalities are defined to summarise values considered as the worst-case.

The worst-case analysis visit will be derived within each treatment period, including scheduled and unscheduled assessments as well as the early termination and follow-up visit assessments. Only post-dose assessments will be considered for the worst-case analysis visit.

5.3 IMPUTATION AND ROUNDING RULES

5.3.1 *Missing values*

[figure not shown]
No imputation of missing values will be done (i.e. observed cases analysis).

5.3.2 *Handling partially or completely missing dates in calculations*

In case of missing date(time)s for FEV₁ assessments, needed for the calculation of AUC_{0-3h}, these cases will be discussed and documented in the DRR.

Partially missing date of first diagnosis event will be imputed as follows for the calculation of time since event:

- Missing day will be imputed with the first day of the month
- Missing day and month will be imputed with 1st JAN

	Statistical Analysis Plan	
CLI-05993AB6-07		Final 1.0 of 22DEC2022

Partially missing date of most recent exacerbation event will be imputed as follows for the calculation of time since event:

- Missing day will be imputed with the last day of the given month
- Missing day and month will be imputed with 31st DEC

5.3.3 *Values below or above a threshold*

Safety values expressed as below (or above) the limit of quantification will be imputed by the value of the quantification limit itself. Listings will always show the non-imputed values.

5.3.4 *Rounding of derived variables*

Derived variables will be rounded at display level:

- AE duration will be presented with 1 decimal.
- Mean of duplicates (blood pressure)/triplicates (ECG) will be rounded to the nearest integer.
Note: since the rounding is applied at display level, in the listings, the change from baseline could be slightly different to the listed value at time point t – baseline value
- Mean of duplicates (lung function) will be rounded to same number of decimal places as the individual values.
Note: since the rounding is applied at display level, in the listings, the change from baseline could be slightly different to the listed value at time point t – baseline value
- FEV₁ AUC_{0-3h} will be rounded to the same number of decimal places as the actual FEV₁ values.
- Relative change from baseline will be presented with 1 decimal.
- Time since first diagnosis and most recent exacerbation will be presented with 1 decimal.

5.3.5 *Outliers*

Potential outliers will be discussed during the review of the data by the Chiesi team. Decisions on whether values are to be excluded from the analysis will be fully documented in the DRR.

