## Study visits

A total of 4 ambulatory study visits and a follow-up call will be performed during the study, as follows:

- A **pre-screening visit** (Visit 0) will be carried out 2 to 7 days before screening, to explain the study, obtain the written informed consent and to instruct the subject on screening visit procedures (e.g. wash-out from medication and restrictions).
- A **screening visit** (Visit 1) will be carried out 2 to 21 days before Treatment period 1 (TP1), to help establishing the eligibility of a subject for inclusion in the study (including routine haematology and blood chemistry, medical history, physical examination, 12-lead electrocardiogram [ECG], lung function, vital signs and training for the use of inhalers). Eligible subjects will continue using their medications (including asthma medications) as needed, ensuring the required wash-out before TP1.

*Note: Visit 0 and Visit 1 can be combined if the study restrictions and wash-out requirements are respected at Visit 0.*

|  |                      |
|--|----------------------|
| Clinical Study Code No.: CLI-05993AB6-07 | Version No.: 2.0     |
| EUDRACT No.: 2022-000536-36              | Date: 30 August 2022 |

- The **investigational phase** comprises two one-day treatment periods, separated by a minimum of 2 days and up to 7 days of wash-out from the study treatment. Each treatment period consists of one ambulatory visit at the investigational centre:
  - **Treatment period 1 (TP1)** including randomisation, followed by a single-dose administration of one of the study treatments (HFA-152a or HFA-134a; according to each subject's randomisation arm) and the assessment of its effects;
  - **Treatment period 2 (TP2)** single-dose administration of the other study treatment and the assessment of its effects.

*Note: For each subject, the study treatment administrations (at TP1 and TP2) will start at approximately the same time of the day.*

During the period of wash-out from the propellant (between TP1 and TP2), subjects will take the asthma medications that were taken before the study start and will ensure the required wash-out period before the administration of the second propellant (at TP2).

- A **follow-up call** (or visit, if deemed necessary by the Investigator) will be performed between 7 and 10 days from TP2.

A subject's participation in the study will end with the follow-up call (or visit, if deemed necessary by the Investigator).

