#### **4.3 Exclusion Criteria**

The presence of any of the following will exclude a subject from study enrolment:

1. **History of “at risk” asthma:** history of near fatal asthma, hospitalisation for asthma in intensive care unit which, in the judgement of the Investigator, may place the subject at undue risk;
2. **Recent exacerbation:** asthma exacerbation requiring systemic corticosteroids or emergency room admission or hospitalisation within 4 weeks prior to screening and prior to randomisation;

|  |                      |
|--|----------------------|
| Clinical Study Code No.: CLI-05993AB6-07 | Version No.: 2.0     |
| EUDRACT No.: 2022-000536-36              | Date: 30 August 2022 |

3. **Asthma requiring use of biologics:** asthma subjects treated with chronic systemic corticosteroids or anti-immunoglobulin E (IgE) or other monoclonal or polyclonal antibodies;
4. **Respiratory disorders other than asthma:** subjects with known respiratory disorders other than asthma. This can include, but is not limited to, diagnosis of COPD as defined by the current guidelines (e.g. Global Initiative for Chronic Obstructive Lung Disease [GOLD] guidelines), known  $\alpha$ 1-antitrypsine deficiency, active tuberculosis, bronchiectasis, sarcoidosis, lung fibrosis, pulmonary hypertension and interstitial lung disease;
5. **Lung cancer or history of lung cancer:** subject with a diagnosis of lung cancer or a history of lung cancer;
6. **Lung resection:** subject with a history of lung volume resection;
7. **Lower respiratory tract infection:** subject with lower respiratory tract infection that required use of antibiotics within 4 weeks prior to screening and prior to randomisation;
8. **Documented coronavirus disease 2019 (COVID-19) diagnosis** within 2 weeks prior to screening, or associated complications/symptoms which have not resolved within 2 weeks prior to screening;
9. **Smoking status:** current smoker, or ex-smoker with a smoking history of  $\geq 10$  pack-years (packyears = the number of cigarette packs per day times the number of years).  
To be eligible for the study, ex-smokers with a smoking history of  $< 10$  pack-years must have stopped smoking for  $\geq 1$  year ( $\geq 6$  months for e-cigarettes);

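### Partial exacerbation dates are imputed as late as possible with no cap at consent, so a descriptive time-since-exacerbation value can be negative

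*SAP*

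**What the plan says.** SAP 4.3.2 defines the variable: "Time since most recent exacerbation (months): (date of ICF – date of most recent exacerbation ended)/30.4375". It sends incomplete dates elsewhere: "Note: Partially missing dates will be imputed as specified in section 5.3.2".

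SAP 5.3.2 gives two rules for this date. For a month-only date: "Missing day will be imputed with the last day of the given month". For a year-only date: "Missing day and month will be imputed with 31st DEC". Neither section sets an upper limit at consent, screening or first dose, and neither says what to do with a negative result. By contrast, the rule for date of first diagnosis in the same section imputes to the earliest possible date.

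SAP 4.3.3 reports the variable by sequence and overall, with "descriptive statistics for time since first diagnosis, time since most recent exacerbation ended and number of exacerbations in the last 12 months". The SAP table list shows Exacerbation History for the Safety set (14.1.2.3.1) and the PP set (14.1.2.3.2). Under SAP 5.4.1 the displayed statistics include the mean, SD, median, minimum and maximum.

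**The concern.** An exacerbation recorded as history at entry should not be shown as ending weeks or months after the subject consented. The two SAP rules, applied together exactly as written, can produce that result. The problem is a stated rule that gives an impossible value, not a lack of detail.

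What is at stake is the credibility of one baseline summary. At most 24 subjects are planned, and only those with a previous exacerbation contribute. A single negative value would be visible as the minimum and would pull the mean down.

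**Working it through.** The plan states no figure on this point to reproduce, so the check applies its own formula to dates.

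**Inputs**
- Formula (SAP 4.3.2): time in months = (ICF date - exacerbation end date) / 30.4375.
- Imputation (SAP 5.3.2): year-only becomes 31 December of that year; month-only becomes the end of that month.
- Consent-to-screening gap (Protocol section 3): 2 to 7 days, or 0 if Visits 0 and 1 are combined.
- Consent dates: assumed, because the documents give none. The examples lie around the protocol v2.0 date (30 August 2022) and the SAP date (22 December 2022).

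**Year-only dates, recorded year 2022, imputed to 31 December 2022**

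| Assumed consent date | Days | Months |
|---|---|---|
| 1 Sep 2022 | -121 | -121 / 30.4375 = -4.0 |
| 1 Oct 2022 | -91 | -91 / 30.4375 = -3.0 |
| 15 Oct 2022 | -77 | -77 / 30.4375 = -2.5 |
| 1 Dec 2022 | -30 | -30 / 30.4375 = -1.0 |

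The sign does not depend on the chosen dates. If the recorded year is the consent year, 31 December is after consent on every consent day except 31 December itself. If the recorded year is earlier, the value is positive: year-only 2021 with consent on 15 October 2022 gives 288 days, or 9.5 months.

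**Month-only dates.** A recorded month of October 2022 with consent on 25 October 2022 gives 25 - 31 = -6 days, or -0.2 months. For a subject who satisfies exclusion criterion 2, an exacerbation of the kind it covers ended more than 28 days before screening. That is at least 29 - 7 = 22 days before consent, even with the longest gap. The event and consent then share a calendar month only if consent falls on day 23 or later. The largest overshoot in a 31-day month is 23 - 31 = -8 days, or -0.3 months. Milder exacerbations, which the criterion does not cover, are not bounded in this way.

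**How often, given a partial date.** Every consent day in 2022 was paired with every end date that was more than 28 days before screening and at most 365 days before consent, for gaps of 0, 2 and 7 days.

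| Gap (days) | Year-only, negative | Month-only, negative |
|---|---|---|
| 0 | 45.8% | 0.0% |
| 2 | 46.0% | 0.0% |
| 7 | 46.7% | 0.3% |

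These shares treat all date pairs as equally likely and are conditional on the date being partial.

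**Effect on the mean.** Let k be the number of contributing subjects (assumed 5 or 10). Replacing one value of -3.0 by the capped value of 0 changes the mean by 3.0 / k: 0.6 months for k = 5 and 0.3 months for k = 10. If the true value were 4.5 months (assumed), the total error in the mean would be (-3.0 - 4.5) / 5 = -1.5 or (-3.0 - 4.5) / 10 = -0.75. Of this, -0.6 or -0.3 comes from the missing cap. The remaining -0.9 or -0.45 comes from the choice of the latest possible date, which a cap leaves in place.

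**The case against.** The best defence is that this is a programming convention for one descriptive variable, and that ordinary checks would catch the result. Protocol section 11 provides front-end and back-end edit checks for consistency, and SAP 5.3.5 sends potential outliers to data review. An event dated after consent would be conspicuous in 24 subjects. Partial dates may also be rare: losing both day and month of an event from the current year is not the usual case. All of this bears on how often the problem would reach a table, and that part stands. It does not correct the rule. The outlier clause only decides whether a value is excluded, which would discard usable history because of an artefact of the derivation. The data review report provision in SAP 5.3.2 covers FEV1 assessment times only.

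A reader might go further and infer that the imputed value could mark an eligible subject as a violation of exclusion criterion 2, which bars certain exacerbations "within 4 weeks prior to screening and prior to randomisation". For example, consent on 10 January 2023 with a year-only date of 2022 gives +10 days, or 0.3 months. The documents do not support that inference. Violations are taken from recorded deviations (SAP 4.2 and Listing 16.2.2.1), and eligibility is checked at screening and at TP1. The derived variable counts from consent, whereas the criterion counts from screening and from randomisation. The criterion also covers only exacerbations needing systemic corticosteroids, emergency room admission or hospitalisation. A short displayed interval is therefore not a finding about eligibility.

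**Conclusion.** The point holds as a minor defect in a stated rule. A year-only exacerbation date in the consent year gives a negative time unless consent is on 31 December; that follows from the SAP's two rules without further assumption. The sizes (such as -3.0 months for consent on 1 October 2022) depend on assumed consent dates, and the mean shifts depend on assumed numbers of contributors. Month-only dates are a much smaller source: 0 to 0.3% of the date pairs examined.

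The consequence stops at Tables 14.1.2.3.1 and 14.1.2.3.2. It would be wrong to read it as a threat to eligibility decisions, PP membership, the FEV1 analyses or the sample size; none of these uses the derived variable.

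**What to change.** Add one sentence to SAP 5.3.2 after the two exacerbation rules: *The imputed date will not be later than the ICF date (use the earlier of the imputed date and the ICF date).* The smallest value that imputation can produce is then 0.0 months. If the recorded month or year is not after that of consent, the capped date stays within it. The cap should act on imputed dates only; a complete date after consent is a data query.

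A further bound placing the date at least 4 weeks before screening should not be added. It can push the date outside what was recorded: year-only 2023 with consent and screening on 16 January 2023 would move to 19 December 2022. It would also presume eligibility and so could hide a real violation.

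The cost is one sentence and one minimum function in the derivation program. Some upward or downward error from imputing a partial date remains, as with any such rule.
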